We will conduct a comparative effectiveness trial that will randomly assign clinicians at participating academic and community practices to one of two different decision support strategies. The first strategy (Registry arm) takes a population health management (PHM) approach and uses a patient registry to identify and track use of CRC screening among older adults for each clinician. The second strategy will enhance the registry by adding an established, multi-faceted SDM training program for clinicians (SDM Skills arm). We will enroll patients of participating primary care providers (PCPs), aged 76-85, who are due or overdue for CRC screening, and survey them shortly after an office visit to determine the impact of the two strategies on outcomes of importance to patients. We plan to randomly assign about 60 participating PCPs to the SDM skills or Registry arms, and enroll about 500 of their eligible patients. We will compare reports of shared decision making, patients' knowledge, and rates of patients who get their preferred option for CRC screening across study arms. We will also compare CRC screening rates across arms and to concurrent and historical controls. Through this project, we will accomplish the following specific aims:

Aim 1: Determine the impact of the approaches on patients' involvement in decision making and knowledge about the risks and benefits of continued CRC screening.

Hypothesis 1.1 (Primary outcome): Patients seen by clinicians in the SDM Skills arm will report more SDM discussions about cancer screening compared to the Registry arm.

Hypothesis 2.1 (Secondary outcome): Patients seen by clinicians in the SDM Skills arm will have higher knowledge of the benefits and harms of CRC screening and treatment compared to Registry arm.

Aim 2: Examine the effects of the interventions on patients' preferences for screening, the extent to which patients receive their preferred approach to screening, and on CRC screening rates.

Hypothesis 2.1 (Secondary outcome): A higher percentage of patients will receive their preferred approach to screening in SDM Skills arm compared to the Registry arm. Hypothesis 2.2: (Secondary outcome) Both interventions will reduce CRC screening rates compared to concurrent controls (rates of clinicians who are not involved in study).

Aim 3: Examine the impact of the interventions on physicians' confidence with and skills for SDM in this setting.

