There is a growing need to address appropriate use of cancer screening tests in older adults. Screening for asymptomatic disease comes with costs and potential harms. Shared decision making (SDM) is an established approach to engaging and informing patients in medical decisions. Currently, there is a lack of evidence on effective interventions to support clinicians in communicating with patients 76-85 about the benefits and harms of cancer screening and tailoring decisions to what matters most to patients. This study will compare two established interventions to advance our understanding of how to support clinicians in conducting SDM conversations with older adults who may be considering stopping cancer screening.

RESEARCH DESIGN AND METHODS

Briefly describe study design and anticipated enrollment, i.e., number of subjects to be enrolled by researchers study-wide and by Partners researchers. Provide a brief summary of the eligibility criteria (for example, age range, gender, medical condition). Include any local site restrictions, for example, "Enrollment at Partners will be limited to adults although the sponsor's protocol is open to both children and adults."

The main study is a cluster randomized trial enrolling about 60 primary care clinicians across all sites. We estimate including about 30-35 clinicians from primary care practices affiliated with Massachusetts General Hospital (MGH) and Brigham and Women's Hospital (BWH), 10-15 from Maine Medical Center (MMC), and 10-15 from community practices affiliated with Newton Wellesley Hospital (NWH) and North Shore Medical Center (NSMC). The participating clinicians at each site will be placed into two groups stratified by gender and years of experience. Then, each group will be randomly assigned to one of two arms: Registry arm or Registry plus SDM Skills training arm (SDM arm). Clinicians in Registry arm will be notified about their patients aged 76-85 who are due for colorectal cancer screening with an upcoming visit. Clinician participants in the SDM arm will also receive the Registry notification and in addition, they will participate in a SDM skills course that includes online training and telephonebased simulated patient interactions.

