After the training, study staff will track and enroll eligible patients who have upcoming visits with participating clinicians in both arms. We plan to enroll about 10 patients per clinician for a total of 500 patients. The clinicians will complete a short survey after each eligible patient visit. The patients will be invited to participate in the survey study and will be asked to complete a survey after their visit and another short survey one year later. Patients will be asked whether a spouse, friend or caregiver was involved in the decision-making process and if so, whether they would be willing to invite them to participate in the study. Study staff will follow up to enroll caregivers that patient participants identify and administer a short survey. We expect that about half of the patients will identify a caregiver, so about 250 caregivers will be surveyed.

Staff will track colorectal cancer screening for 12 months after the recorded date of visit for participating patients, for participating clinicians and for non-participating clinicians across these sites to examine trends in screening over time. Historical controls will also be collected to calculate rates of screening across the sites for the 2 years prior to the study (approximately calendar years 2017 and 2018).

The eligibility criteria for the clinician and patient participants are in Tables 1 and 2.

Table 1: Eligibility for clinician participants		
Eligible	Ineligible	
 Primary Care Physician (MD or NP) Have ≥20 potentially eligible patients in their panel Use of Epic electronic health record 	 Residents, medical students 	

	Table 2: Eligibility for	patient participants
--	--------------------------	----------------------

Eligible	Ineligible
 Adults, age 76-85 at the time of a scheduled visit Scheduled for non-urgent office visit with a participating clinician during the study period Due or overdue for colorectal cancer screening (e.g. never been screened, <1 year to follow-up interval indicated on last test). 	 Prior diagnosis of colon or rectal cancer, inflammatory bowel disease or genetic disorder that raises CRC risk (hereditary non-polyposis CRC and familial adenomatous polyposis) Unable to consent for themselves (moderate to severe dementia or other major cognitive limitations) Unable to read or write in English or Spanish

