- b. Compared to the Comparator group, patients seen by physicians in the Intervention arm would have greater knowledge: We will use linear regression with GEE to compare the mean knowledge score between the two arms. The target sample size will provide 80% power to detect a difference of 0.28 SD for the knowledge scores after adjusting for the effects of clustering. Although there are no standards for a minimally important difference in knowledge, SDM studies have found effect sizes of 0.25SD-0.8SD in studies of decision aids, and this study is adequately powered to detect a meaningful difference in that range, and
- Examine the effects of the interventions on patients' preferences for screening, the extent to which patients receive their preferred approach to screening, and on CRC screening rates.

- a. Compared to the Comparator group, patients seen by physicians in the Intervention arm will receive their preferred approach to screening (either colonoscopy, stool-based test, or no further screening). For these analyses, we will compare the percentages of patients who prefer to stop screening, the percentages of informed patients who received their preferred screening in the 12 months after the visit, and overall rates of screening across the two groups using logistic regression model with the GEE approach to adjust for clustering of patients within clinicians. We will have 81% power to detect a difference of 14% in rates (e.g. decrease from 61% to 47%).
- b. Both interventions will reduce screening rates compared to concurrent controls (rates of clinicians not involved in study). The screening data will be available for all patients from all participating sites. We estimate a total of 6248 patients will be eligible for screening from 436 clinicians: 5353 patients from clinicians not participating the study and 448 from each arm of clinicians participating the study. After taking into account clustering effect, we will have at least 86% power to detect a 6% decrease in CRC screening rates of patients from clinicians participating.
- 3. Examine the effects of the interventions on physicians' confidence and demonstration in their SDM skills and their satisfaction.

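### SAP hypothesis 2b compares targeted volunteer clinicians with non-participants without a stated model, site term or prior screening rate, and its 86% power fits only pooled arms

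*SAP*

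**What the plan says.** The SAP (Statistical methods, hypothesis 2b) states: "Both interventions will reduce screening rates compared to concurrent controls (rates of clinicians not involved in study". Protocol Hypothesis 2.2 makes the same claim. The SAP counts "5353 patients from clinicians not participating the study and 448 from each arm of clinicians participating the study" and, after an unspecified clustering allowance, claims "at least 86% power to detect a 6% decrease in CRC screening rates of patients from clinicians participating". Hypothesis 2b gives no regression model, covariates, reference rate, ICC or sidedness. The logistic GEE model is named under 2a, for comparing the two arms.

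The protocol (study procedures; Clinician recruitment) has investigators seek out clinicians with many eligible patients and those in community health centers or more diverse settings. Those clinicians then opt in. Recruitment Procedures gives current screening rates of 52%-65% across sites.

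The protocol also plans for earlier data. Specific Aims says "We will also compare CRC screening rates across arms and to concurrent and historical controls". Research Design and Methods says "Historical controls will also be collected to calculate rates of screening across the sites for the 2 years prior to the study", meaning about 2017 and 2018, and has screening tracked for participating clinicians and "for non-participating clinicians across these sites to examine trends in screening over time". The paragraph on clinician, practice and network screening rates has data aggregated down to the physician. It covers the historical and concurrent periods and study and non-study clinicians, with limited patient characteristics. The SAP refers to the protocol for methods but never mentions historical rates.

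**The concern.** Randomisation protects the comparison between arms. It does not protect a comparison of either arm, or both, with clinicians who never joined. Those who were targeted and volunteered may already have screened people aged 76-85 more or less often than their colleagues. With no site term and no earlier rate in the analysis, such a gap goes straight into the estimated effect. A gap in one direction looks like a reduction, and a gap in the other direction conceals one. The hypothesis is worded causally, so the risk is a causal conclusion drawn from a volunteer comparison.

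The unit of comparison is also unclear. Naming both interventions suggests one test per arm, while the power sentence refers to participating clinicians as a single group. The choice changes the power substantially.

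**Working it through.** **Inputs.** From SAP 2b: 448 patients per arm (896 pooled), 5353 controls, a 6-point decrease, and 6248/436 = 14.33 patients per clinician. Borrowed, because 2b gives none: ICC 0.03 and two-sided 5% (SAP Sample Size, for the SDM Process score), a 61% reference rate (the 2a example), and 52% and 65% as the ends of the protocol's site range.

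**1. Reproducing the stated power.** Divide each group by DE = 1 + (m - 1) x ICC and use a pooled-variance z test: power = Φ[(d - z s0)/s1]. Here s0 = √[p̄(1 - p̄)(1/n1 + 1/n2)] and s1 = √[p1(1 - p1)/n1 + p2(1 - p2)/n2]. Example, pooled, 61% to 55%, DE 1.40: n1 = 640, n2 = 3824, s0 = 0.0209, s1 = 0.0212, so power is 81.5%. Power (%) at reference rates 52 / 61 / 65:

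| Contrast | No clustering | ICC 0.015, DE 1.20 | DE 1.27 | ICC 0.03, DE 1.40 |
|---|---|---|---|---|
| Pooled, two-sided 5% | 91.4 / 92.2 / 93.0 | 86.0 / 87.0 / 88.1 | 84.0 / 85.1 / 86.3 | 80.3 / 81.5 / 82.9 |
| One arm, two-sided 5% | 68.5 / 70.1 / 71.7 | 60.6 / 62.3 / 64.0 | 58.2 / 59.9 / 61.6 | 54.1 / 55.8 / 57.5 |
| Pooled, one-sided 5% | 95.4 / 95.8 / 96.3 | 91.8 / 92.4 / 93.2 | 90.5 / 91.1 / 91.9 | 87.9 / 88.7 / 89.6 |
| One arm, one-sided 5% | 78.8 / 79.9 / 81.1 | 72.1 / 73.4 / 74.7 | 69.9 / 71.3 / 72.7 | 66.3 / 67.6 / 69.1 |

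DE 1.27 is the primary outcome's design effect (500/394, or 1 + 9 x 0.03). The pooled contrast reaches about 86% by several routes. One arm never does, even with no clustering and a one-sided test.

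**2. Effect of a pre-existing gap (illustration).** Assume no true effect, a 61% control rate, 60 participating and 436 - 60 = 376 other clinicians, and a participant rate already 2 points lower. Then P(false reduction) = Φ(gap/SE - 1.96), with SE² = 0.59 x 0.41 x DE1/n1 + 0.61 x 0.39 x DE2/5353.
- ICC 0.02: DE1 = 1.279, DE2 = 1.265. Pooled SE = 0.0200, giving 16.8%. One arm: SE = 0.0273, giving 11.0%.
- ICC 0.03: DE1 = 1.418, DE2 = 1.397. Pooled SE = 0.0211, giving 15.6%. One arm: SE = 0.0288, giving 10.3%.

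The nominal rate in this direction is 2.5%. If the gap runs the other way, a true 6-point reduction appears as 4 points, and pooled power falls from 80%-84% to 47%-51%.

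**3. Could site alone matter?** The protocol lists 190 + 108 + 128 = 426 clinicians and plans 30-35 participants from MGH and BWH. Take 35 of 60 participants (58.3%) against 155 of 366 others (42.3%), with site rates at opposite ends of the 13-point range. The contrast shifts by 0.160 x 13 = 2.1 points. Adding 10 BWH clinicians to match the SAP's 436 gives 1.9. This is an extreme case, since no site-specific rates are given.

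**4. How much would the earlier rate remove?** If clinician effects are stable, adjusting for an earlier rate based on n patients removes a share λ = n x ICC/[1 + (n - 1) x ICC] of a gap between clinicians. With n assumed to be 15-40 (no denominator is given), λ runs from 0.30/1.28 = 0.23 (n = 15, ICC 0.02) to 1.20/2.17 = 0.55 (n = 40, ICC 0.03). A 2-point gap shrinks to between 1.5 and 0.9 points.

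**The case against.** The strongest reply is that the SAP already provides for adjustment. Statistical methods says regression was used to adjust for unbalanced variables, and that sentence comes before the whole list of hypotheses, 2b included. The protocol adds the historical comparison, the look at trends and the patient characteristics. What is missing is therefore a model statement, not data or design. This is partly right. However, the adjustment sentence directly follows a comparison of patient characteristics between arms and depends on observed imbalance. It mentions neither non-participants nor site nor earlier rates. It does not clearly reach 2b, and the protocol supplies no model either.

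Second, pooling can largely be inferred, since the power sentence treats participants as one group and only pooling fits the figure. That stands, and a clarifying sentence is enough. A reader might go further and infer that the 86% is a miscalculation. The documents do not support that: a pooled test reaches it with a smaller ICC, with the primary outcome's design effect at a 65% reference rate, or with a one-sided test.

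Third, the gap sizes, the screening ICC and the historical denominators are assumed. That also stands, and step 2 shows sensitivity, not expected bias.

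**Conclusion.** The concern holds as an incomplete analysis specification for one secondary hypothesis, and the sponsor should correct it. 2b sets targeted volunteers against non-participants and does not say how a pre-existing difference would be separated from an effect, although suitable data were planned. A 2-point gap would raise the false-reduction rate from 2.5% to about 16%-17% pooled (10%-11% for one arm), given the assumed 61% base rate and ICC 0.02-0.03. The 86% power supports a pooled claim only. A per-arm claim has 54.1%-57.5% two-sided power at ICC 0.03, and at most about 81% under the most favourable assumptions (one-sided 5%, no clustering).

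A reader might infer that the 2b result is biased, or biased towards a reduction. The documents give neither the size nor the direction of any gap, so that does not follow. Nor does the point touch the primary outcome or the randomised comparison in 2a.

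**What to change.** For 2b, specify a model that allows for clustering by clinician and adjusts for site, the clinician's own 2017-2018 screening rate and the patient characteristics already collected. If earlier rates turn out to exist only by site, adjust for site alone and say so. State that the arms are pooled; if they are to be tested separately, restate the power. Report the unadjusted contrast as descriptive and label any 2b conclusion as non-randomised evidence. The SAP is dated July 2022, enrolment ended in April 2021 and tracking ran for 12 months, so mark the change as made after both.

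The cost is SAP wording and one model, provided the physician-level rates exist. The benefit is limited. On the assumptions in step 4, the earlier rate removes only about 23%-55% of a gap, and adjustment does not deal with clinicians selected on their trend. The power of the full adjusted model cannot be computed, because the documents give no correlation between earlier and later rates and no site-specific rates. A difference-in-differences analysis is an optional sensitivity check, and it relies on parallel trends through COVID-19.

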Study Title: Promoting informed decisions about colorectal cancer screening in older adults

(PRIMED Study): A cluster randomized trial

**Document Title:** Design and Analysis plan for the cluster randomized trial in the PRIMED Study

PIs: [name] ([contact]) and [name] ([contact]) Statisticians: [name]; [name]

Clinical Trials.gov: NCT03959696

**Date:** July 27, 2022

*Purpose:* The goal of the study was to advance our understanding of how to ensure that older adults are well-informed and involved in decisions about whether or not to continue CRC screening. Refer to the study protocol for an outline of the methods used in the study.

*Design:* The PRIMED study is a multi-site cluster randomized trial that enrolled primary care physicians and assigned them to Intervention or Comparator arms. The Intervention arm involved completion of a CME-provided 2-hour online training course in SDM communication skills and received an electronic reminder of patients with an upcoming appointment who are eligible for a CRC screening discussion. Comparator arm physicians received electronic reminders only. Each clinician will complete a baseline survey and a telephone-based SPI to capture baseline SDM skills before patient enrollment begins. Patients and physicians were surveyed after an eligible visit to assess outcomes. After enrollment is complete, all clinicians will participate in a debrief interview.

Physicians were recruited from internal medicine and family medicine practices affiliated with five hospital networks—three academic medical centers and two community hospitals—located in Massachusetts and Maine. They were eligible if they had at least 20 patients aged 75-85 due for a CRC screening or surveillance in their panel. Physicians were enrolled from May to August 2019.

Patients were enrolled from October 2019 through April 2021 (due to COVID-19, patients were

not enrolled from March 13, 2020-May 24, 2020). Eligibility criteria for patient participants are

listed in Table 1.

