  - a. Compared to the Comparator group, physicians in the Intervention arm will report higher confidence in their SDM skills: Clinician confidence will first be analyzed as a continuous variable. Variable transformation will be performed to improve normality assumption if deemed necessary. Additionally, we will dichotomize the

variable into very or extremely confident vs. not. A two-sample t-test or Wilcoxon rank sum test, as appropriate, will be used to compare the continuous outcome while a chi square test will be used to compare the dichotomized outcome. With a sample size of 50 clinicians, we will have 81% power to detect difference of 35%, e.g. from 50% to 85%, in the percentage of clinicians who are very or extremely confident in different elements needed to conduct SDM conversations. In our prior study of the SDM skills webinar, we found a 30-40% absolute increase in clinician confidence.

- b. Compared to the Comparator group, physicians in the Intervention arm will demonstrate more SDM skills in the SPI: We will code each transcript using Braddock's Informed Decision Making framework that covers core aspects of SDM (scores range from 0 to 9). First, we will determine whether a two-sample t-test or a Wilcoxon rank sum test is more appropriate to compare the two groups. Assuming the score is normally distributed, a sample size of 25 in each group will have 80% power to detect a 0.81SD difference in the mean Braddock score (or about 1.4 points out of 9). Our prior study of a 3-hour CME online SDM skills webinar, we found an increase of 1.2SD on the Braddock scale after training.
- c. Compared to the Comparator group, physicians in the Intervention arm will report higher satisfaction with the visit. The percentage of clinicians who report that they are extremely satisfied with the visit will be compared across arms using a chisquare test.
- 4. Examine the effects of the interventions on **caregivers' SDM Process scores**: Caregivers who attended a visit with an eligible patient (and for whom the patient provided contact

information) were invited to complete a post-visit survey. They were asked to complete an adapted version of the SDM Process survey to provide their perspective on the conversation and involvement of the patient. A total score will range from 0-4, with higher scores indicating more shared decision making. These analyses are exploratory.

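### The 86% power in SAP hypothesis 2b cannot hold for each arm at the documents' screening rates and is under-specified for the arms pooled; the non-randomised comparison also has no model using the planned historical rates

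*SAP*

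**What the plan says.** SAP, Statistical methods, hypothesis 2b: "Both interventions will reduce screening rates compared to concurrent controls (rates of clinicians not involved in study"). The planned numbers follow: "We estimate a total of 6248 patients will be eligible for screening from 436 clinicians", made up of "5353 patients from clinicians not participating the study and 448 from each arm of clinicians participating the study". After a clustering allowance whose size is not given, the SAP concludes that "we will have at least 86% power to detect a 6% decrease in CRC screening rates of patients from clinicians participating".

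The other inputs stand elsewhere and are not tied to 2b:

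- ICC 0.03 and two-sided 0.05 are given in the SAP's Sample Size paragraph, for the SDM Process score only.
- The screening rates in the documents are 52%-65% for patients aged 76-85 at these sites (Protocol, Recruitment Procedures) and the 61% starting point of an example in SAP 2a.
- SAP 3a plans on 50 participating clinicians; the protocol says about 60.
- The outcome could be the share of patients up to date (Protocol, section on clinician, practice and network level rates) or any test within 12 months of the index visit (SAP, Patient Outcomes). 2b does not say which.

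On the comparison, Protocol, Specific Aims announces concurrent and historical controls. Research Design and Methods collects rates for the two years before the study, about 2017 and 2018. The section on screening rates aggregates them by physician for the historical and concurrent periods, for study and non-study clinicians. The SAP does not mention historical rates. The logistic GEE in 2a compares the two randomised groups, and 2b names no model.

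**The concern.** 2b is worded as a claim about both interventions and gives a count for each arm, so a reader can take the 86% as the power for each arm. The power sentence itself speaks of participating clinicians' patients without naming an arm, which fits a pooled contrast. The two readings differ by a factor of two in the smaller group, and the smaller group dominates the variance here.

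If the per-arm reading is adopted and is false, a non-significant arm would be taken as good evidence against a 6-point fall when the study had far less than 86% power to show one.

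The second matter is bias. Clinicians volunteered, and those with many eligible patients were targeted (Protocol, study procedures and Clinician recruitment). If their screening rates already differed from their colleagues' before the study, a concurrent comparison alone cannot separate that difference from an intervention effect. The documents give no figure for its size.

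**Working it through.** **Inputs.** 448 per arm, 896 pooled, 5353 controls, 436 clinicians (SAP 2b; the parts sum to 6249, not 6248, which has no effect here). The 6% is read as percentage points: a relative 6% of 61% is 3.7 points, and pooled power would then be only 54% even without clustering. Assumed for 2b because it is silent: control rate p1 of 52%-65%, p2 = p1 - 0.06, alpha 0.05.

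**Formula.** Divide each n by its design effect DE = 1 + (m - 1) x ICC, where m is patients per clinician. Power = Phi[(0.06 - z x SE0)/SE1], with SE1 = sqrt(p1(1-p1)/n1 + p2(1-p2)/n2). SE0 is the null standard error from the pooled proportion, or SE1 in the unpooled version. z = 1.960 two-sided, 1.645 one-sided. Ranges below cover 52%-65% and both versions.

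**Design effects.**

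- Primary outcome: 500/394 = 1.27, which is 1 + 9 x 0.03, or about 10 patients per clinician.
- 2b's own counts: 6248/436 = 14.3, so 1 + 13.33 x 0.03 = 1.40.
- 50 participating clinicians: 896/50 = 17.9, so 1.51; their 386 non-participating colleagues have 5353/386 = 13.9, so 1.39.

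**Trying to reproduce the 86%.** Pooled arms, DE 1.27, 61% against 55%: n2 = 896/1.27 = 706, n1 = 5353/1.27 = 4218, SE0 = 0.0199, SE1 = 0.0202. Power = Phi[(0.06 - 1.96 x 0.0199)/0.0202] = Phi(1.04) = 85%. Over 52%-65% it is 84.0-86.3%, the closest two-sided match. The same DE also comes close to 2a: 250/1.27 = 197 per arm, 61% against 47%, gives about 80% against a stated 81%. So 1.27 may have been carried over, but the SAP does not say so.

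**Per arm, no clustering, 61% against 55%.** SE0 = 0.0240, SE1 = 0.0244, so power = Phi[(0.06 - 0.0471)/0.0244] = Phi(0.53) = 70%.

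| Case | Per arm, two-sided | Pooled, two-sided | Pooled, one-sided |
|---|---|---|---|
| No clustering | 68.5-71.7% | 91.4-93.0% | 95.4-96.3% |
| DE 1.27 | 58.2-61.6% | 84.0-86.3% | 90.5-92.0% |
| ICC 0.03, 14.3 per clinician | 54.1-57.5% | 80.3-82.9% | 87.8-89.6% |
| ICC 0.03, 17.9 per participating clinician | 51.1-54.8% | 77.3-80.6% | 85.7-87.9% |

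The last row covers DE 1.51 in both groups and 1.51 with 1.39. Using 1.51 and 1.39, pooled one-sided power is 86.0-87.9%.

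**Limits of each reading.**

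- Per arm, one-sided, no clustering: at most 81.1%.
- Per arm, two-sided, no clustering: 86% needs a control rate of about 26% or lower, or 82% or higher.
- Pooled, two-sided: 86% needs an ICC no higher than 0.015-0.021 at 14.3 patients per clinician, or 0.012-0.017 at 17.9.

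**Sensitivity to the counts.** Of physicians, the SAP says: "They were eligible if they had at least 20 patients aged 75-85 due for a CRC screening or surveillance in their panel". Fifty such panels hold at least 1000 patients, not 896, though the definitions may differ. With 1000 at ICC 0.03, two-sided power is 80.1-82.7% pooled and 53.9-57.4% per arm. With 60 x 20 = 1200, pooled power is 85.6-87.7%, and per arm it is still at most 82.1% without clustering.

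**The case against.** The strongest reply is that the pooled figure has not been refuted. 2b is directional, its sidedness is unstated, and a one-sided 0.05 test with the SAP's own ICC and 50 participating clinicians gives 86.0-87.9%, which fits the claim over the whole 52%-65% range. A smaller ICC would also do it. This stands. A reader might infer that the 86% is an arithmetic error, or that the chance of missing a 6-point fall is really 17-23% instead of at most 14%. The documents do not support the first. The second holds only for a two-sided pooled test at ICC 0.03 with 14.3-17.9 patients per clinician; one-sided on the same inputs it is about 10-14%.

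It is also fair that ICC 0.03 was given for a different outcome, and that 52%-65% are current site rates which may not match 2b's denominator or measure. The per-arm limit is therefore conditional on those rates. It does not depend on the ICC or on sidedness.

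On the comparison, Hypothesis 2.2 in the protocol names only concurrent controls, and 2b matches it. No document calls for a clinician-level baseline covariate, so that part is a recommendation. One might infer that the SAP plans an unadjusted analysis. It only names no model, and its general sentence on adjusting for unbalanced variables follows a between-arm comparison of patient characteristics, so it does not clearly reach this contrast. The Specific Aims do promise a historical comparison, and the SAP leaves it out.

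Finally, 2b is secondary and did not set the sample size. That limits the consequence but does not supply the missing inputs.

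**Conclusion.** The point holds in two parts.

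First, the power statement cannot be interpreted as written. If the documents' 52%-65% rates apply, at least 86% is out of reach for each arm: at most about 72% two-sided or 81% one-sided with no clustering, and about 51-58% two-sided at ICC 0.03. For the arms pooled it is under-specified: 84-86% two-sided at DE 1.27, about 77-83% two-sided at ICC 0.03 with 14.3-17.9 patients per clinician, and about 86-90% one-sided on those last inputs. All of this assumes a 6-point decrease, alpha 0.05 and 2b's group sizes.

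Second, 2b is a non-randomised comparison of self-selected clinicians with their colleagues. The SAP gives it no model and no use of the historical rates that the protocol plans to collect. The size of any resulting bias cannot be estimated from the documents.

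This should be fixed, but it does not touch the primary outcome. Confidence is medium, because the sponsor's actual inputs are not visible.

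**What to change.** 1. **Power statement.** State which contrast the 86% refers to, with its ICC, patients per clinician, control rate, sidedness and screening measure. Do not apply it to each arm. If it was two-sided at ICC 0.03 and 52%-65%, restate it as about 77-83% for both arms pooled and 51-58% for each arm. If other inputs were used, give them and the power that follows.
2. **Analysis of 2b.** Specify a logistic GEE clustered by clinician, with group (two arms and non-participants), site, and each clinician's 2017-2018 screening rate on the same measure as a covariate. Keep the concurrent controls: "Patients were enrolled from October 2019 through April 2021", and the 12-month follow-up ran through COVID-19, so historical rates alone would not serve. Report 2b as a non-randomised comparison, with confidence intervals for each arm and for both pooled.
3. **Timing.** The SAP is dated July 2022, after enrolment ended. Fix the model before the 2b rates are compared, or label it post hoc.

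The cost is SAP wording and one covariate from data that the protocol already plans to collect; the sample does not change. The downsides are a possibly less favourable power figure, the need for a rule for clinicians without 2017-2018 rates, and volunteer bias that a baseline rate does not remove.
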